#### ▪ **Samples Receipt, Check and Storage by the Analytical Unit**

- The Person responsible for the study or designated person from the analytical area will receive samples (along with documentation) and check 100 % with the assistance from analysts and Quality Assurance. They will record any remarks on the appropriate form. Once review is finished the person responsible for the study or designated person will store samples in the ultra-freezer documenting it on the equipment's notebook.
- Quality Assurance will confirm accuracy and reliability of operations.

Samples which do not meet acceptance criteria will be rejected, according with the Manual of Operations Reception, storage, handling matrix and biological samples.

(see Manual of Operations). In addition to those which don't have documentation along with them. In such instances, the clinical unit should be informed about the reason why samples were rejected. Rejected biological specimens will be kept at the analytical unit until the analytical unit and the clinical unit make an agreement about their disposition.

Further details e.g. on the collection, processing, labeling, and shipping of the samples will be detailed in the trial Manual of Operations (MOP).

- **Handling of Biological Specimens by the Analytical Unit**

Biological specimens will be handled and processed as described in the appropriate analytical technique.

- **Biological Specimens Disposition**

As agreed with the Sponsor or 30 calendar days following the final report, samples will be removed from the ultra-freezer and will be stored in a transient warehouse for infectious biological hazard residues until they are collected for their final disposition by an authorized designated company.

- **Ultra-frozen Samples Labeling**

Cryotubes will be identified with labels according to the standard operating procedure, code: **PP** [REDACTED], **EARLY ORGANIZATION FOR THE CONDUCT OF DAN** INTERCHANGEABILITY AND BIOCOMPARABILITY STUDY. Each cryotube will state the study number, subject's number, period and number of samples specified in the protocol. Labels will be digitally designed and printed using thermal printer. Label and printing type will ensure that that printing and adhesion resist several freezing and thaw cycles.

## **9 Pharmacokinetic and statistical analysis**

Pharmacokinetics and statistical analysis of Metformin and Gliclazide's plasma concentrations will be conducted by the analytical unit from the **PPD** [REDACTED], according to their standard operating procedures and in accordance with the NOM-177-SSA1-2013.

Pharmacokinetic parameters (non-compartmental analysis) and statistical analysis for determining the food effect on bioavailability will be calculated using Phoenix WinNonlin 6.3 software.

### **9.1 Sample Size**

According to the goals for the study treatment regarding postprandial/fasting, pharmacokinetic parameters will be calculated AUC and  $C_{max}$  for both analytes, Metformin and Gliclazide. In order to have an accurate and reasonable precision for the estimated ratios, 22 subjects will be randomized.

Taking 90 % confidence interval for the postprandial/fasting ratio as a measure for accuracy and assuming an average variation coefficient of 20 % for AUC (AUC0-∞, AUC0-t) and Cmax for Metformin or Gliclazide, then with 18 evaluable subjects the food effect on pharmacokinetics can be estimated with an accuracy of 12 %. The following ratio will be carried out, being R the estimated ratio and LCL / UCL lower and higher confidence levels for the 90% confidence interval for R:

$$0.89 * R \leq LCL < UCL \leq 1,12 * R$$

An accuracy of 12% will result in an accurate description for the food effects. Besides, 18 evaluable subjects are enough to detect a difference among treatments of 18 % or higher with a power of 80 % at least. Taking into account a drop-out rate around 20 %, 22 subjects should be randomized.

## **9.2 Randomization**

Valid statistical inferences are generally derived by assuming that errors in the observations are distributed independently, in random variables. Randomization generally ensures validity of this hypothesis. Full randomization of subjects to the treatment's sequence will be made according to the design sequences based on the internal procedures from the PPD

compliant with the Mexican Official Standard NOM-177-SSA1-2013 using the randomization.com software.

A total of 22 subjects are to be enrolled in the trial and randomized to one of 2 treatment sequences, such that 11 subjects are assigned to each treatment sequence. Male and female subjects will be included. Every effort will be made to reach gender balance (at least 40 % for each gender).

Once it is confirmed that all inclusion criteria and none exclusion criteria have been met, a consecutive number in ascendant order will be assigned to subjects, starting by 1 up to the last case (22), as described in sections 7.3 and 7.4, and according with the SOP code: PPD, RANDOMIZATION IN AN INTERCHANGEABILITY AND BIOCOMPARABILITY CLINICAL STUDY.

## **9.3 Outcome variables**

### **9.3.1 Main outcome variable**

To assess the food effect on bioavailability the pharmacokinetics metrics going to be AUC0-∞, AUC0-t and Cmax for Metformin and Gliclazide, given as single dose in fasting state and postprandial conditions.

### **9.3.2 Secondary outcome variables**

- Additional pharmacokinetic parameters will be determined: t1/2, tmax, Vz/f and CL/f.
- To assess and compare safety and tolerability of the fixed dose combination metformin /Gliclazide administered in fasting and fed state.

## 9.4

## Deviation and Exclusion to the Statistical Analysis

All deviations should be justified with statistical or scientific data and any change to the original statistical plan should be documented, in the study master file and in the pharmacokinetics statistical report as well as in the final study report. Subjects' data will not be replaced. Any missing data will not be replaced. Likewise, data cannot be removed from the statistical analysis, except in the following events.

- **Research Subjects with Pre-dose Concentrations in the Biological Matrix**

In the event pre-dose concentration is less than 5 % of the  $C_{max}$  value for a research subject, subject's data can be included. When pre-dose value is greater than 5 % of the  $C_{max}$ , research subjects data should be removed from all study of food effect on bioavailability.

- **Exclusion of data due to vomit or diarrhea.**

Data from research subjects who experience vomiting and diarrhea throughout the study for immediate release products can be removed from the statistical analysis if vomiting and diarrhea occur before 2 fold the median for  $t_{max}$  or 2 fold  $t_{max}$  value obtained from the research subject in a given period.

- **Research subject with very low plasma concentrations for study drugs.**

As established by NOM-177-SSA1-2013, research subjects in a cross designed who provide evaluable data for test drug and reference drug, or who do not have evaluable data in the single period of a parallel design, should not be either included in the statistical analysis.

It is considered that a research subject has very low concentrations, if the AUC is lower than 5 % of the geometric means for the reference drug's AUC (it should be calculated without including outliers). Exclusion of data due to this reason will only be accepted prior scientific rationale and review of the case by the COFEPRIS.

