**PREPARATION AND ADMINISTRATION OF DRUGS IN INTERCHANGEABILITY AND BIOCOMPARABILITY CLINICAL STUDIES.**

A subject is compliant with the treatment only if he/she completes both study periods.

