### Statistical Analysis

This trial intends to estimate the effect of food on pharmacokinetics. It is not intended to prove or confirm statistically the lack of any food effect.

Therefore, no statistical hypothesis is presented. As primary analysis, a mixed model will be applied for all  $C_{max}$ ,  $AUC_{0-t}$  and  $AUC_{0-\infty}$  for Metformin and  $C_{max}$ ,  $AUC_{0-t}$  and  $AUC_{0-\infty}$  for Gliclazide, of the fixed dose combination metformin /Gliclazide log transformed. With TREATMENT, PERIOD and SEQUENCE as fixed effects, and the SUBJECT (SEQUENCE) as random effect.

Based on the residual error term 90 % confidence intervals will be built for the estimated differences postprandial - fasting, resulting in 90 % confidence intervals for postprandial/fasting ratios following the repeated transformation.

Statistical comparisons between treatments A and B, with respect to  $C_{max}$ ,  $AUC_{0-t}$ , and  $AUC_{\infty}$  of Metformin/Gliclazide, will in each case separate based on a mixed linear model for log transformed (natural log) pharmacokinetic parameter data. For each parameter evaluation and each pairwise comparison, the statistical model will include covariate adjustments for period and sequence as fixed effects, and subject, nested within sequence as random effect. Carry-over effects will be assumed ignorable.

General linear model for the analysis of variance, representing the experimental design, will be used for the analysis of data for pharmacokinetic variables by considering the additive form for the following variation sources:

- ✚ Dosing sequence.
- ✚ Subjects nested in the dosing sequence called variability or residual value between subjects.
- ✚ Dosing period.
- ✚ Treatment or formulation.
- ✚ Experimental error, called variability or residual value between subjects.

That general linear model, applied to the crossed designs to determine the food effect on bioavailability is as follows:

$$Y_{ijk} = \mu + G_k + S_{jk} + P_j + F_{(j,k)} + e_{ijk} \quad (\text{Chow \& Liu, 2009})$$

Where:

$\mu$  = overall mean

$G_k$  = fixed effect of  $k^{th}$  sequence

$S_{jk}$  = randomized effect of the  $i^{th}$  subject in the  $k^{th}$  sequence, where  $i = 1, 2, \dots, n_k$  y  $k = 1, 2, \dots, K$

$P_j$  = fixed effect of the  $j^{th}$  period, where  $j = 1, 2, \dots, J$  y  $\sum_j P_j = 0$

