8.1 Interim Analysis

To assess food influence on the study drug assessed, a crossed 2-period and 2-sequence design was used, with a sampling time of 168 hours which allowed to estimate the 90% of the average AUC for the analytes.

The pharmacokinetic analysis for the plasma concentrations was performed using the WinNonlin® software with a non-compartmental model and the use of real times.

The t_{\max} and C_{\max} values were obtained from the measures taken. The area under the curve of plasma concentration from t_0 (dosing) to the t_n ($AUC_{0 \rightarrow t}$), was estimated with the trapezoidal method with lineal interpolation. To determine the area under the curve from the last sampling time to the infinite time ($AUC_{t \rightarrow \infty}$), the last plasma concentration quotient in the clearance rate was determined by lineal regression, using the sampling points from the terminal lineal logarithm which fitted the best to the straight line. The $AUC_{0 \rightarrow \infty}$ was determined adding up the $AUC_{0 \rightarrow t}$ and the $AUC_{t \rightarrow \infty}$.

The statistical analysis was performed with the WinNonlin® using the least squares with the generalized lineal model (GLM).

The intra-subject Student residual analysis for the pharmacokinetic parameters was performed with Microsoft Excel®.

The following model was used for the analysis:

$$Y_{ijkl} = \mu + S_k + V(S)_{i(k)} + P_j + F_l + e_{ijkl} \dots \dots \text{ (Chow \& Liu, 2009)}$$

Where:

Y_{ijkl}	is the response (pharmacokinetic parameter) in the i^{th} volunteer, where j is the $-^{\text{th}}$ period, and k^{th} sequence with l^{th} treatment.
μ	is the overall mean.
S_k	is the effect of the k^{th} dosing sequence.
$V(S)_{i(k)}$	is the of the i^{th} volunteer in the k^{th} sequence, which is considered a randomized effect.
P_j	is the effect of the j^{th} period (or dosing phase).
F_l	is the effect of the l^{th} treatment or formulation.
e_{ijkl}	is the experimental error, intra-volunteer variability and a randomized effect assumed with normal distribution, zero media, constant variance and independent of the volunteer's effect sequentially nested.

Based on the determination of the average square error and the determination of the geometric means, the classic 90% confidence intervals estimation was made for the test-reference ratio in the previously logarithmic transformed data. Where the test corresponds to the post-prandial conditions and the reference to fasting conditions.

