10.1 Definition of Protocol Deviations and Analysis Sets

All deviations should be justified with statistical or scientific data and any change to the original statistical plan should be documented, in the study master file and in the pharmacokinetics statistical report as well as in the final study report. Subjects' data will not be replaced. Any missing data will be considered as non-existent data. Likewise, data cannot be removed from the statistical analysis, except in the following events.

- **Research Subjects with Pre-dose Concentrations in the Biological Matrix**

In the event pre-dose concentration is $< 5\%$ of the C_{max} value for a research subject, subject's data can be included without any adjustment to measurement and pharmacokinetic calculations. When pre-dose value is $> 5\%$ of the C_{max} , research subject should be removed from all study bioequivalence assessments.

- **Exclusion of data due to vomit or diarrhea.**

Data from research subjects who experience vomiting and diarrhea throughout the bioequivalence study for immediate release products can be removed from the statistical analysis if vomiting and diarrhea occur before 2 fold the median for t_{max} or 2 fold t_{max} value obtained from the research subject in a given period.

- **Research subject with very low plasma concentrations for study drugs.**

As established by NOM-177-SSA1-2013, research subjects in a cross designed who provide evaluable data for test drug and reference drug, or who do not have evaluable data in the single period of a parallel design, should not be either included in the statistical analysis.

It is considered that a research subject has very low concentrations, if the AUC is lower than 5 % of the geometric means for the reference drug's AUC (it should be calculated without including outliers). Exclusion of data due to this reason will only be accepted prior scientific rationale and review of the case by the COFEPRIS.

11

General Specifications for Statistical Analyses

Pharmacokinetic parameters (non-compartmental analysis) and statistical analysis for determining bioequivalence will be calculated using Phoenix WinNonlin 8.0 software.

The results of this trial will be reported using summary tables, figures, and data listings, as appropriate. All data will be summarized by treatment and/or scheduled time point, as appropriate.

12

Protocol Deviations

12.1

Important Protocol Deviations

Not applicable. No deviation was observed in the study

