13.1 Demographics

Table 13.1. Demographic Variables' Individual Data

Case	Sex	Age	Weight	Height	BMI	Sequence
PPD						

Table 13.2. Demographic Variables' Descriptive Statistics

Statistics	Age (years)	Weight (kg)	Height (m)	BMI (Kg/m ²)
Mean	PPD			
SD				
Median				
25th percentil				
75th percentil				
Minimum				
Maximum				

14**Treatment Compliance and Exposure**

All subjects receive the investigational treatment at the pre-specified fixed dosage. Information relating to the extent of exposure is thus contained in the treatment labelling.

15**Endpoint Evaluation****15.1****Primary Endpoint Analyses**

The determination of pharmacokinetics parameters were determined using WinNonlin software depending of their own characteristics as follows:

C_{max}: is the peak or maximum concentration

AUC_{0-t}: area under de curve computed from time zero to the time of the last positive Y value.

AUC_{0-∞}: area under de curve computed from time zero to extrapolated from infinity.

Ke: First-order rate constant associated with the terminal (log-linear) elimination phase. This is estimated via linear regression of time vs. log concentration.

Primary pharmacokinetics parameters, AUC and C_{max}, were used to estimate the effect of food on pharmacokinetics. It is not intended to prove or confirm statistically the lack of any food effect.

As primary analysis, a mixed model will be applied for all C_{max}, AUC_{0-t} and AUC_{0-∞} for Metformin and C_{max}, AUC_{0-t} and AUC_{0-∞} for Gliclazide, of the fixed dose combination metformin /Gliclazide log transformed. With TREATMENT, PERIOD and SEQUENCE as fixed effects, and the SUBJECT (SEQUENCE) as random effect.

Based on the residual error term 90 % confidence intervals will be built for the estimated differences postprandial - fasting, resulting in 90 % confidence intervals for postprandial/fasting ratios following the repeated transformation.

Statistical comparisons between treatments A and B, with respect to C_{max} , AUC_{0-t} , and AUC_{∞} of Metformin/Gliclazide, will in each case separate based on a mixed linear model for log transformed (natural log) pharmacokinetic parameter data.

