Table 15.4.3. Gliclazide's Pharmacokinetic Parameters Results for Fasting Conditions.

Gliclazide Fasting Conditions									
Variable	N	Mean	SD	CV%	Min	Median	Max	Geo Mean	Geo CV%
Cmax	PPD								
Tmax									
Lambda_z									
HL_Lambda_z									
AUClast									
AUCINF_obs									
AUC_%Extrap_obs									
Cl_F_obs									
Vz_F_obs									
MRTINF_obs									

Table 15.4.4. Gliclazide's Pharmacokinetic Parameters Results for Fed Conditions.

Variable	N	Gliclazide Fed Conditions							
		Mean	SD	CV%	Min	Median	Max	Geo Mean	Geo CV%
Cmax	PPD								
Tmax	PPD								
Lambda_z	PPD								
HL_Lambda_z	PPD								
AUClast	PPD								
AUCINF_obs	PPD								
AUC_%Extrap_obs	PPD								
Cl_F_obs	PPD								
Vz_F_obs	PPD								
MRTINF_obs	PPD								

PPD									

15.5

Other Endpoint Analyses

Data about plasma concentration versus time for each subject, as well as the descriptive statistics are shown in tables 15.5.1 and 15.5.2 for metformin, with a dosing schedule of the test drug, R for fasting state and T for post-prandial state. Gliclazide's concentrations for both conditions are shown in tables 15.5.1 and 15.5.2.

Table 15.5.1. Individual concentrations table corresponding to metformin in fasting state. n = P volunteers

Form	Volunteer	Time																				
		0.0	0.5	1.0	2.0	3.0	4.0	5.0	6.0	7.0	8.0	10.0	12.0	16.0	24.0	28.0	32.0	48.0	72.0	96.0	120.0	144.0
PPD																						

Table 15.5.2 Individual concentrations table for metformin in post-prandial state. n = **P** volunteers

[REDACTED]
[REDACTED]

BD1412-63CEC
EMR200763-004

Bioavailability of a Metformin/Gliclazide fixed combination tablet
Version 1.0

Form	Volunteer	Time																					
		0.0	0.5	1.0	2.0	3.0	4.0	5.0	6.0	7.0	8.0	10.0	12.0	16.0	24.0	28.0	32.0	48.0	72.0	96.0	120.0	144.0	168.0

PPD

PPD

Table 15.5.3. Individual concentrations table for gliclazide in fasting state. n = P volunteers

Form	Volunteer	Time																				
		0.0	0.5	1.0	2.0	3.0	4.0	5.0	6.0	7.0	8.0	10.0	12.0	16.0	24.0	28.0	32.0	48.0	72.0	96.0	120.0	144.0
PPD																						

Table 15.5.4 Individual concentrations table for gliclazide in post-prandial state. n = 21 volunteers

Form	Volunteer	Time																				
		0.0	0.5	1.0	2.0	3.0	4.0	5.0	6.0	7.0	8.0	10.0	12.0	16.0	24.0	28.0	32.0	48.0	72.0	96.0	120.0	144.0
PPD																						

PPD

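### The evaluable-data exclusion rule has lost its negation: as written, it removes the crossover subjects who have usable fed and fasted data

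*Protocol*

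**What the plan says.** Protocol 9.4 states that data may be removed from the statistical analysis only in listed circumstances. One of these, placed under the item on very low plasma concentrations and attributed to NOM-177-SSA1-2013, names "research subjects in a cross designed who provide evaluable data for test drug and reference drug" and says that such subjects are not to be analysed.

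The sentence recurs in SAP 10.1, which defines deviations and analysis sets, and in SAP 12.2, which lists reasons for exclusion from an analysis set. Both halves can be read together there: "who provide evaluable data for test drug and reference drug, or who do not have evaluable data in the single period of a parallel" design. Nothing elsewhere in either document corrects it.

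Other parts of the plan bear on its meaning:

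- Protocol 9.5, on the primary comparison: "Based on the residual error term 90 % confidence intervals will be built for the estimated differences postprandial - fasting".
- Protocol 9.1, on sample size: "18 evaluable subjects are enough to detect a difference among treatments of 18 % or higher".
- Protocol 7.9, on compliance: "A subject is compliant with the treatment only if he/she completes both study periods".
- SAP 8.1, on test and reference: "Where the test corresponds to the post-prandial conditions and the reference to fasting conditions".
- SAP 15.1, on the model: "With TREATMENT, PERIOD and SEQUENCE as fixed effects, and the SUBJECT (SEQUENCE) as random effect".

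**The concern.** The two halves of the sentence lead to the same consequence, exclusion, but set opposite conditions. The parallel-design half excludes subjects without evaluable data. The crossover half excludes subjects with evaluable data under both treatments. Only the crossover half applies to this trial.

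Subjects measured in both conditions supply the within-subject fed/fasted ratio and the residual error behind its 90 % CI. The written rule removes exactly those subjects.

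Two things are at stake. First, the list of permitted exclusions is closed and the SAP repeats it as its analysis-set definition, so the definition of who enters the primary comparison is wrong in both governing documents. Second, no other item on the list deals with incomplete pairs. With this one inverted, there is no valid written rule for a subject evaluable in only one condition. SAP section 8 reports 22 randomized and 21 finished, so that case may have arisen.

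**Working it through.** **1. The wording, side by side**

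| Half of the sentence | Condition as written | Consequence | Applies here? |
|---|---|---|---|
| Crossover | provides evaluable data for test and reference | not analysed | Yes, the design is 2x2 crossover |
| Parallel | does not have evaluable data in its single period | not analysed | No |

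The wording is the same in all three places, with no redaction or broken table inside the sentence, so this is not an artefact of reading the PDF.

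**2. Consistency with the rest of the plan**

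- SAP 8.1 defines test as fed and reference as fasted, so the crossover half means subjects evaluable in both conditions.
- Protocol 9.1 builds the sample size on 18 evaluable subjects. Under the literal rule, evaluable subjects are the ones removed.
- Protocol 7.9 makes completing both periods the condition for compliance.
- SAP Table 16.2 lists a T/R ratio for each subject, which requires both periods.
- SAP Table 15.5.4 is labelled "Individual concentrations table for gliclazide in post-prandial state. n = 21 volunteers", which suggests the literal rule was not applied.

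If all 21 finishers were evaluable in both conditions (an assumption), the literal rule leaves 21 − 21 = 0 pairs. With the negation restored, it leaves up to 21.

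**3. The plan's own precision figure**

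Inputs from Protocol 9.1: CV 20 %, 18 evaluable subjects, 90 % CI, stated limits 0.89R and 1.12R. The CV is taken as intra-subject.

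- Log-scale SD: s = sqrt(ln(1 + 0.20²)) = 0.1980
- Half-width: t(0.95, n − 2) × s × sqrt(0.5 × (1/n1 + 1/n2))
- n = 18 (9/9): 1.7459 × 0.1980 × 0.3333 = 0.1153, so 0.891R to 1.122R. This reproduces the stated limits.
- n = 21 (11/10): 1.7291 × 0.1980 × 0.3090 = 0.1058, so 0.900R to 1.112R. This assumes that all 21 finishers are evaluable in both periods.

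The planned precision therefore does not depend on the faulty sentence.

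**4. What the corrected rule would cost**

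The mixed model has subject as a random effect, so it could use one-period data that the corrected rule leaves out. To size this, suppose the 22nd subject had one evaluable period (the documents do not say). Compare the generalized-least-squares SE of the log ratio from 21 pairs (11/10) with that from 21 pairs plus one single-period subject in the smaller sequence. Treatment, period and sequence are fixed effects. The between-subject CVs are assumptions; the documents give none.

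| Between-subject CV | SE, 21 pairs | SE, 21 pairs + 1 | Increase from leaving the subject out |
|---|---|---|---|
| 10 % | 0.06119 | 0.06060 | 1.0 % |
| 30 % | 0.06119 | 0.06096 | 0.4 % |
| 50 % | 0.06119 | 0.06108 | 0.2 % |

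Restricting the model to complete pairs costs almost nothing.

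**The case against.** The strongest reply is that this is a self-evident slip. A rule that removes every usable pair cannot be applied by mistake, the rest of the plan makes the intent clear, and no figure changes. That stands as a limit on the weight of the point. It does not remove the defect: an analysis-set definition in a protocol and a SAP should not state its opposite, and the recoverable intent does not by itself supply a written rule for incomplete pairs.

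Four narrower objections have force:

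- The n = 21 label belongs to one concentration listing (gliclazide, fed), and the results tables are redacted. It indicates that the literal rule was not used, but does not show who entered the fed/fasted model.
- The one-period calculation prices the corrected rule, not the missing word, and rests on assumed between-subject CVs.
- If subject is fitted as a nested effect in the least-squares model of SAP 8.1, a one-period subject adds nothing to the treatment contrast. The extra line proposed for SAP 15.1 then only makes explicit what the restored rule already implies.
- The cited standard was not available for this check, so any replacement sentence is a reconstruction from the context.

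**Conclusion.** The concern holds. The crossover half of the rule is inverted in Protocol 9.4, SAP 10.1 and SAP 12.2, and the inversion is uncorrected. Confidence is high that the rule is wrong as written. The exact replacement wording is inferred from the parallel-design half and the rest of the plan, and needs checking against the standard.

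There is no effect on planned precision. The consequence is that the written definition of the primary comparison's population is unusable and does not agree with the analysis planned around it. This should be corrected, but it gives no ground for doubting the sample size.

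**What to change.** In SAP 10.1 and SAP 12.2, and in Protocol 9.4, replace the sentence with wording such as: *Subjects who do not provide evaluable data in both the fed (test) and the fasted (reference) period are not included in the fed/fasted comparison.* Check this against NOM-177-SSA1-2013 and delete the parallel-design clause, which has no application here.

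Add one line to SAP 15.1: *The primary model is fitted to subjects with evaluable data in both periods.*

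The SAP already reports the trial as conducted, so the practical route is to correct the SAP and record the correction in the study report. Any formal edit to the protocol text would go through the change procedure in Protocol 11.5.

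The cost is one sentence in three places and one added line. The only downside is that any single-period data leave the ratio model, with the small loss of precision shown above.
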